4.7.3.1.2 INTRA-OPERATIVE

Data collected during procedure:

- Overall Operating Room (OR) time;
- Duration of procedure (first incision to skin closure);
 - Includes time to completion of resection (capturing the time thoracoscopic camera is inserted until the specimen is received);
- Procedure data:
 - Location of affected lobe;
 - Number of pulmonary arteries (1, 2, or 3+);
 - Confirm visualization of the cut line indicator field prior to transection;
 - Confirm presence or absence of calcified hilar lymph nodes;
 - Use of other stapling devices for bronchus and

parenchyma transection (number and color of cartridges);

- Number of ports;
- Intra-operative surgical interventions (not associated with transection of the PA/PV), if applicable;
- Reason for conversion to open surgery, if applicable;
- Volume of estimated intra-operative blood loss;
- Transfusion products (and rationale for use), if applicable;
- Concomitant procedures/interventions performed, if applicable;
- Number of chest tubes placed and anatomic position;
- Tumor size and TNM staging, if available;
- Intra-operative interventions/procedures on PA/PV to stop bleeding, if applicable:
 - Hemostasis intervention: bleeding detected and controlled intra-operatively (additional stapling, over-sewing, clip placement, compression, use of suture, sealant, and/or buttress, and/or use of energy); or bleeding that occurs intra-operatively requiring blood or blood product transfusion or an additional surgical procedure (e.g. conversion to open).
- Device usage data:
 - Usability and articulation questions;
- Surgeon Device Questionnaire (**PVS procedures only**);
- Surgeon Satisfaction Questionnaire (**SOC and PVS procedures**);
- SURG-TLX (**SOC and PVS procedures**);
- Adverse Events;
- Pain medications given perioperative (i.e. spinal block, intercostal nerve blocks, etc.); and
- Concomitant medication (associated with AEs and pain)

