10.10 Additional Endpoint Analyses

Device usage details will be summarized with counts and percentages for subjects in whom the device was articulated during the surgical procedure. Summaries will be provided by randomized treatment group and in total. Similar summaries will also be provided for the surgeon satisfaction questionnaire and the surgeon device questionnaire (administered only in PVS cases).

Post-operative pain is assessed at Visit 3 and Visit 4. Subjects are asked to rate their pain on a scale ranging from 0 (no pain) to 10 (worst possible pain). Subjects will rate pain relating to three sites – trocar site, incisional site, and chest tube site. Summary statistics will be provided at Visits 3 and 4, as well as the change from Visit 3 to Visit 4. No inferential comparisons between treatment groups are planned.

Summary statistics will be provided for the Surgery Task Load Index (Surg-TLX). Surgeons are asked to rate 6 specific components after each surgery performed. The 6 components are – mental fatigue, physical fatigue, hurried/rushed pace, procedure complexity, anxious while performing procedure, and distracting operating environment. Each component is scored on a 0 to 100 scale with lower scores representing a ‘Low’ response on that component and higher scores indicating a ‘High’ response on that component. Summaries will also be provided for an overall score which is calculated as the average of the six components for each surgery.

The ASES Shoulder Assessment is a patient reported outcome designed to measure functional limitations and pain of the shoulder and has been adapted to this study to measure upper body functionality following VATS lobectomy. The assessment utilizes 10 questions that are answered with: unable to do = 0, very difficult to do = 1, somewhat difficult to do = 2, and not difficult = 3. Scores for each subject are obtained by summing the responses to the 10 questions and thus range from 0 to 30. Summary statistics will be provided for the ASES Shoulder Assessment at Visit 1 (prior to surgery), Visit 3 (after surgery, prior to discharge), and Visit 4 (approximately 4 weeks after surgery). Summary statistics will also be provided for the change from Visit 1 to Visit 3, and for the change from Visit 1 to Visit 4.

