Sponsor Assessment of Protocol Deviations [1]			
Minor	xx (xx.x%)	xx (xx.x%)	xx (xx.x%)
Major	xx (xx.x%)	xx (xx.x%)	xx (xx.x%)
Number (%) of Subjects With at Least 1 Protocol Deviation [2]	xx (xx.x%)	xx (xx.x%)	xx (xx.x%)

1. Denominator used is the total number of protocol deviations reported.
2. Denominator used is the total number of subjects in the column header.

Table 4
 Surgical Characteristics
 Full Analysis Set

Characteristics	Standard of Care Stapler (N = ##)	Powered Vascular Stapler (N = ##)	Overall (N = ##)
Location of Affected Lobe			
Left Lung, Superior Lobe	xx (xx.x%)	xx (xx.x%)	xx (xx.x%)
Left Lung, Inferior Lobe	xx (xx.x%)	xx (xx.x%)	xx (xx.x%)
Left Lung, Multiple Lobes	xx (xx.x%)	xx (xx.x%)	xx (xx.x%)
Right Lung, Superior Lobe	xx (xx.x%)	xx (xx.x%)	xx (xx.x%)
Right Lung, Middle Lobe	xx (xx.x%)	xx (xx.x%)	xx (xx.x%)
Right Lung, Inferior Lobes	xx (xx.x%)	xx (xx.x%)	xx (xx.x%)
Right Lung, Multiple Lobes	xx (xx.x%)	xx (xx.x%)	xx (xx.x%)
Calcified Hilar Lymph Nodes Present?			
Yes	xx (xx.x%)	xx (xx.x%)	xx (xx.x%)
No	xx (xx.x%)	xx (xx.x%)	xx (xx.x%)
Number of Pulmonary Arteries Transected			
0	xx (xx.x%)	xx (xx.x%)	xx (xx.x%)
1	xx (xx.x%)	xx (xx.x%)	xx (xx.x%)
2	xx (xx.x%)	xx (xx.x%)	xx (xx.x%)
3	xx (xx.x%)	xx (xx.x%)	xx (xx.x%)
Number of Ports			
1	xx (xx.x%)	xx (xx.x%)	xx (xx.x%)
2	xx (xx.x%)	xx (xx.x%)	xx (xx.x%)
3	xx (xx.x%)	xx (xx.x%)	xx (xx.x%)
4	xx (xx.x%)	xx (xx.x%)	xx (xx.x%)
Number of Chest Tubes Placed Intraoperatively			
0	xx (xx.x%)	xx (xx.x%)	xx (xx.x%)
1	xx (xx.x%)	xx (xx.x%)	xx (xx.x%)
2	xx (xx.x%)	xx (xx.x%)	xx (xx.x%)
ASA Physical Status			
Class I	xx (xx.x%)	xx (xx.x%)	xx (xx.x%)
Class II	xx (xx.x%)	xx (xx.x%)	xx (xx.x%)
Class III	xx (xx.x%)	xx (xx.x%)	xx (xx.x%)

Table 4
 Surgical Characteristics
 Full Analysis Set

Characteristics	Standard of Care Stapler (N = ##)	Powered Vascular Stapler (N = ##)	Overall (N = ##)
Estimated Blood Loss (mL)			
n	XX	XX	XX
Mean	XX.X	XX.X	XX.X
Standard Deviation	X.XXX	X.XXX	X.XXX
Median	XX.X	XX.X	XX.X
Minimum, Maximum	XX.X, XX.X	XX.X, XX.X	XX.X, XX.X
Transfusion of Blood or Blood Product Required?			
Yes	XX (xx.x%)	XX (xx.x%)	XX (xx.x%)
No	XX (xx.x%)	XX (xx.x%)	XX (xx.x%)
Procedure Converted to Open?			
Yes	XX (xx.x%)	XX (xx.x%)	XX (xx.x%)
No	XX (xx.x%)	XX (xx.x%)	XX (xx.x%)
Procedure Duration (min)			
n	XX	XX	XX
Mean	XX.X	XX.X	XX.X
Standard Deviation	X.XXX	X.XXX	X.XXX
Median	XX.X	XX.X	XX.X
Minimum, Maximum	XX.X, XX.X	XX.X, XX.X	XX.X, XX.X
Chest Tube Duration (nights)			
n	XX	XX	XX

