Same summary will be repeated for:

Incisional Pain
 Chest Tube Pain

Programming note: Change from Visit 3 to Visit 4 will be calculated as Visit 4 value minus Visit 3 value.

Note: For each pain component, the subject is asked to rate his or her pain today on a scale from 0 (no pain) to 10 (worst possible pain).

Table 12
Surgeon Device Questionnaire
Full Analysis Set

Question Response	Powered Vascular Stapler (N = ##)

The ECHELON FLEX Powered Vascular Stapler with Advanced Placement Tip enables easier placement of the device on vessels compared to your current standard of care device:
 
Strongly Disagree Slightly Disagree Neutral Agree Strongly Agree
	
xx (xx.x%) xx (xx.x%) xx (xx.x%) xx (xx.x%) xx (xx.x%)

The ECHELON FLEX Powered Vascular Stapler with Advanced Placement Tip has the potential to reduce the amount of dissection required (otomy) around the vessel to place the stapler compared to your current standard of care device:
 
Strongly Disagree Slightly Disagree Neutral Agree Strongly Agree
	
xx (xx.x%) xx (xx.x%) xx (xx.x%) xx (xx.x%) xx (xx.x%)

The ECHELON FLEX Powered Vascular Stapler with Advanced Placement Tip has the potential to reduce the surgeon stress during the most challenging step of the procedure, which is the pulmonary artery / pulmonary vein transection, compared to your current standard of care device:
 
Strongly Disagree Slightly Disagree Neutral Agree Strongly Agree
	
xx (xx.x%) xx (xx.x%) xx (xx.x%) xx (xx.x%) xx (xx.x%)

The ECHELON FLEX Powered Vascular Stapler with Advanced Placement Tip allows for the precise control and placement of the end effector on the target vessel compared to your current standard of care device:
 
Strongly Disagree Slightly Disagree Neutral Agree Strongly Agree
	
xx (xx.x%) xx (xx.x%) xx (xx.x%) xx (xx.x%) xx (xx.x%)

Table 13
 ASES Shoulder Assessment
 Full Analysis Set

Shoulder Side	Time Point Statistic	Standard of Care Stapler (N = ##)	Powered Vascular Stapler (N = ##)	Overall (N = ##)
Right	Visit 1			
	n	XX	XX	XX
	Mean	XX.X	XX.X	XX.X
	Standard Deviation	X.XXX	X.XXX	X.XXX
	Median	XX.X	XX.X	XX.X
	Minimum, Maximum	XX.X, XX.X	XX.X, XX.X	XX.X, XX.X
	Visit 3			
	n	XX	XX	XX
	Mean	XX.X	XX.X	XX.X
	Standard Deviation	X.XXX	X.XXX	X.XXX
	Median	XX.X	XX.X	XX.X
	Minimum, Maximum	XX.X, XX.X	XX.X, XX.X	XX.X, XX.X
	Change From Visit 1 to Visit 3			
	n	XX	XX	XX
	Mean	XX.X	XX.X	XX.X
	Standard Deviation	X.XXX	X.XXX	X.XXX
	Median	XX.X	XX.X	XX.X

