	Minimum, Maximum	XX.X, XX.X	XX.X, XX.X	XX.X, XX.X
	Visit 4			
	n	XX	XX	XX
	Mean	XX.X	XX.X	XX.X
	Standard Deviation	X.XXX	X.XXX	X.XXX
	Median	XX.X	XX.X	XX.X
	Minimum, Maximum	XX.X, XX.X	XX.X, XX.X	XX.X, XX.X
	Change From Visit 1 to Visit 4			
	n	XX	XX	XX
	Mean	XX.X	XX.X	XX.X
	Standard Deviation	X.XXX	X.XXX	X.XXX
	Median	XX.X	XX.X	XX.X
	Minimum, Maximum	XX.X, XX.X	XX.X, XX.X	XX.X, XX.X

Same summary will be repeated for: Left Side

Programming note: Change from Visit 1 to Visit 3 will be calculated as Visit 3 value minus Visit 1 value.

Table 14
 Adverse Events by System Organ Class and Preferred Term
 Safety Set

System Organ Class	Preferred Term	Standard of Care Stapler (N = ##)	Powered Vascular Stapler (N = ##)	Overall (N = ##)
Total		xx (xx.x%)	xx (xx.x%)	xx (xx.x%)
System Organ Class 1	Preferred Term 1	xx (xx.x%)	xx (xx.x%)	xx (xx.x%)
	Preferred Term 2	xx (xx.x%)	xx (xx.x%)	xx (xx.x%)
	Preferred Term 3	xx (xx.x%)	xx (xx.x%)	xx (xx.x%)
System Organ Class 2	Preferred Term 1	xx (xx.x%)	xx (xx.x%)	xx (xx.x%)
	Preferred Term 2	xx (xx.x%)	xx (xx.x%)	xx (xx.x%)
System Organ Class 3	Preferred Term 1	xx (xx.x%)	xx (xx.x%)	xx (xx.x%)
	Preferred Term 2	xx (xx.x%)	xx (xx.x%)	xx (xx.x%)
	Preferred Term 3	xx (xx.x%)	xx (xx.x%)	xx (xx.x%)
System Organ Class 4	Preferred Term 1	xx (xx.x%)	xx (xx.x%)	xx (xx.x%)
	Preferred Term 2	xx (xx.x%)	xx (xx.x%)	xx (xx.x%)

The following tables will have the same format as Table 14:

Table 15	Serious Adverse Events by System Organ Class and Preferred Term Safety Set
Table 16	Adverse Events Related to the Study Device by System Organ Class and Preferred Term Safety Set
Table 17	Serious Adverse Events Related to the Study Device by System Organ Class and Preferred Term Safety Set
Table 18	Adverse Events Related to the Study Procedure by System Organ Class and Preferred Term Safety Set
Table 19	Serious Adverse Events Related to the Study Procedure by System Organ Class and Preferred Term Safety Set

Table 20
 Adverse Events by System Organ Class, Preferred Term and Maximum Severity
 Safety Set

System Organ Class	Preferred Term	Standard of Care Stapler (N = ##)	Powered Vascular Stapler (N = ##)	Overall (N = ##)
Total		xx (xx.x%)	xx (xx.x%)	xx (xx.x%)
Mild		xx (xx.x%)	xx (xx.x%)	xx (xx.x%)
Moderate		xx (xx.x%)	xx (xx.x%)	xx (xx.x%)
Severe		xx (xx.x%)	xx (xx.x%)	xx (xx.x%)
System Organ Class 1		xx (xx.x%)	xx (xx.x%)	xx (xx.x%)
Mild		xx (xx.x%)	xx (xx.x%)	xx (xx.x%)
Moderate		xx (xx.x%)	xx (xx.x%)	xx (xx.x%)

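### SAP Table 13 summarises ASES by right and left shoulder, so each block pools operated-side and non-operated-side shoulders; an operated-side panel would be a cheap improvement

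*SAP*

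**What the plan says.** SAP 5.3 lists ASES among the key additional endpoints. SAP 10.10 explains that the instrument "has been adapted to this study to measure upper body functionality following VATS lobectomy". It defines the score in one sentence, "Scores for each subject are obtained by summing the responses to the 10 questions and thus range from 0 to 30", and asks for summary statistics "for the change from Visit 1 to Visit 3, and for the change from Visit 1 to Visit 4". The text of 10.10 does not mention side.

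Side appears only in the Table 13 shell. Its row variable is "Shoulder Side", the first block is for the right shoulder, and the shell closes with "Same summary will be repeated for: Left Side". Columns are the two randomized arms and overall, on the Full Analysis Set.

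The side of surgery is available. Protocol 4.7.3.1.2 collects "Location of affected lobe". SAP Table 4 tabulates it with categories such as "Left Lung, Superior Lobe" and "Right Lung, Superior Lobe". Every Table 4 category, including the two for multiple lobes, names one lung, and inclusion criterion 5 (Protocol 4.2.1) refers to a single operated lung.

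Nothing else in the SAP regroups shoulders by operated side. SAP 10.8 plans no subgroup analyses, and none of the 24 named listings is for ASES.

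**The concern.** The instrument was brought in to describe function after a one-sided operation, and the natural first question is how the shoulder on the side of surgery changed. A right/left split does not answer that directly. The right block contains operated-side shoulders from right-sided cases and opposite-side shoulders from left-sided cases; the left block is the reverse.

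If the two shoulders respond differently, three things follow. The mean change in each block lies between the operated-side and opposite-side changes. The spread of change scores within a block grows, because two populations are mixed. And the arm comparison within a block depends partly on whether the arms happen to have the same share of right-sided operations. The randomization described in SAP section 3 is balanced within site, and no balancing by operated side is mentioned.

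**Working it through.** The documents state no ASES effect size, standard deviation or precision, so there is no figure of the plan to reproduce.

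**Inputs**
- r, the share of right-sided operations: not given. Assumed 0.4 to 0.6.
- d_op, the mean change in the operated-side shoulder: not given.
- d_non = c × d_op, the mean change in the other shoulder: c is not given. Assumed 0 (unaffected), 0.5 (half as much) and 1 (equal).
- About 100 subjects per arm: SAP section 8 (about 200, randomized 1:1).
- A simplifying assumption that right-sided and left-sided operations have the same effect on their own side.

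**What each block shows**

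Right mean = r × d_op + (1 − r) × d_non, so the fraction of d_op shown is r + (1 − r)c.

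Left mean = (1 − r) × d_op + r × d_non, so the fraction is (1 − r) + rc.

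| r | c | Right block | Left block |
|---|---|---|---|
| 0.4 | 0 | 40% | 60% |
| 0.5 | 0 | 50% | 50% |
| 0.6 | 0 | 60% | 40% |
| 0.4 | 0.5 | 70% | 80% |
| 0.5 | 0.5 | 75% | 75% |
| 0.6 | 0.5 | 80% | 70% |
| any | 1 | 100% | 100% |

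The same fractions apply to an arm difference in operated-side change, if c is read as the ratio of the two sides' arm differences and r is the same in both arms.

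**Added spread**

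Mixing variance within a block = r(1 − r)(d_op − d_non)². As an illustration only, take r = 0.6, d_op = −6 points and d_non = 0. The right block shows 0.6 × (−6) = −3.6 and the left block 0.4 × (−6) = −2.4. The added variance is 0.6 × 0.4 × 36 = 8.64 points squared. Without an ASES standard deviation, that cannot be called large or small. In relative terms, if the operated-side effect is one standard deviation, c = 0 and r = 0.5, the standard deviation in a block rises by a factor of √(1 + 0.25) = 1.12.

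**Chance imbalance in operated side**

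With no device effect, the arm difference in the right block = (r_PVS − r_SOC) × (d_op − d_non), and the left block shows the same size with the opposite sign. For a 10-percentage-point imbalance and c = 0, operated-side drops of 3, 5 and 8 points give spurious differences of 0.3, 0.5 and 0.8 points. With c = 0.5 these halve to 0.15, 0.25 and 0.4; with c = 1 they vanish. Treating allocation as simple, the standard error of the imbalance at r = 0.5 is √(2 × 0.5 × 0.5 / 100) = 0.071, so 10 points is about 1.4 standard errors and would not be unusual.

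**The case against.** The strongest objection is that the harm depends on a premise the documents never state. SAP 10.10 describes the target as upper-body function, not operated-side function, and nowhere says that the shoulder on the side of surgery is affected more. A reader might infer that the layout dilutes any surgical or arm effect. The documents do not support that: with c = 1 there is no dilution, and with c = 0.5 most of the effect remains. This stands, and the point is worded conditionally for that reason.

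A reader might also infer that the operated-side change is lost from the table. That goes too far. The right and left means add up to d_op + d_non; in the illustration, −3.6 + (−2.4) = −6. Lobe location by arm is in Table 4, so r is known. When r is not 0.5 the two equations can be solved: at r = 0.6, d_op = 3 × Right − 2 × Left = −10.8 + 4.8 = −6. This stands in part. The solution fails at r = 0.5, can magnify sampling error through the multipliers, and relies on equal effects of right-sided and left-sided operations. SAP 10.1 and the appendix introduction also promise listings of all collected data, which would allow shoulders to be linked to lobe location, although no ASES listing is named.

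Nor does the point bear on the trial's conclusion. SAP section 6 sets no hypotheses and no p-values, so a loss of power would concern a test nobody plans. The acceptance criterion uses firings only. The arms differ in the stapler used on the pulmonary vessels, and the documents give no mechanism by which that would alter shoulder function. This stands in full.

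Finally, a change is not free. SAP 10.1 requires an amendment when planned analyses change, and parts of the SAP are written in the past tense, in an open-label study. Replacing the right/left layout or naming a new main summary at that stage would be a late redefinition. This argues for adding a panel instead of substituting one.

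**Conclusion.** The point holds as a conditional, low-severity improvement. It is certain from the documents that each Table 13 block pools operated-side and non-operated-side shoulders, and that no planned output separates them. How much this matters is not certain. Under an assumed 40 to 60% of right-sided operations, a block shows 40 to 60% of the operated-side effect if the other shoulder is unaffected, 70 to 80% if it changes half as much, and all of it if both change equally. A 10-point laterality imbalance would add a spurious 0.3 to 0.8 points for drops of 3 to 8 points in the first case, half that in the second and nothing in the third. The laterality share, the size of the drop and the response of the other shoulder are all assumptions.

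The present layout does not show directly which of these cases applies; a panel by operated side would. The primary endpoints and the 3% acceptance criterion are untouched.

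**What to change.** 1. Derive operated and non-operated shoulder for each subject from the affected-lobe field already collected under Protocol 4.7.3.1.2 (left-lung category: left shoulder is operated side; right-lung category: right shoulder).
2. State that rule in SAP 10.10, and say there that the 0 to 30 score is computed separately for each shoulder, as the Table 13 shell implies.
3. Add to Table 13 a panel for operated and non-operated side, by arm and overall, with change from Visit 1 to Visit 3 and from Visit 1 to Visit 4. Keep the right and left blocks as a supplement.

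The cost is one derived variable, one extra panel and a short SAP amendment under SAP 10.1, dated and recorded as a late addition. No new data are needed. If both shoulders turn out to change equally, the added panel loses nothing and shows that.
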